Approximately 30–35 centers will participate in the study in the United States/North America. This study consists of up to five study periods:

- Screening Period
- Immunization Study Period

Group A: Immunization Study Period and OCR treatment starts at Day 1/Week 1. Patients will receive 300 mg of open-label OCR on Day/Week 1 (Dose 1 Infusion 1) and Day 15/Week 2 (Dose 1 Infusion 2). Patients in Group A will be split and be assigned to either Group A1 (booster 13-PCV) or Group A2 (influenza vaccine). At Day 85/Week 12 patients will start to receive immunizations and undergo post-immunization assessments. For all patients in Group A, the Immunization Study Period will end on Day 169/Week 24.

Group B: Patients will not receive OCR. At Day 1/Week 1, patients will start to receive immunizations and undergo post-immunization assessments. For Group B, the Immunization Study Period will end at Day 84/Week 12.

The timing of immunizations and post-baseline assessments are detailed in [Appendix 1](#).

[figure not shown]
- Optional OCR Extension (OOE) Period:
 - **Groups A1 and A2:** Patients who complete the 24-week immunization study period will have the option for retreatment with a single infusion of 600 mg OCR (Dose 2) at Day 169/Week 24 and subsequent single infusions (600 mg OCR) at intervals of 24 weeks provided that he or she meets the OOE retreatment criteria and chooses to receive retreatment.
 - **Group B:** Patients who complete the 12-week immunization study period will have the option to receive OCR in the OOE; the first dose will be administered as two single infusions of 300 mg, on Day 84/Week 12 (Dose 1 Infusion 1) and Day 98/Week 14 (Dose 1 Infusion 2), and subsequent doses will be administered as single 600 mg infusions (Dose 2, Dose 3, etc.) at intervals of 24 weeks provided that he or she meets the OOE retreatment criteria and chooses to receive retreatment. Group B patients who do not qualify for and/or do not choose treatment with OCR at Week 12 will complete the study at Week 12 and will **not** enter safety follow-up.

Please note that the OOE will continue with all patients who are able to receive OCR as per local guidelines, or unless the Sponsor decides to terminate the OCR program for MS; however, the OOE will not exceed 4 years after the last patient last visit in the Immunization Study Period. *At the end of the OOE, patients may choose to continue on commercially available OCR.*

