4.4.2.5 Seasonal Influenza Vaccine

The influenza vaccine is indicated for immunization against influenza caused by the influenza strains included in the vaccine. The inactivated (or recombinant) vaccine has

been chosen for this study to assess antibody production for a commonly used clinically relevant antigen.

Group A2 patients can receive the influenza vaccine at any time between Day 85/Week 12 and Day 140/Week 20.

Group B patients will receive the influenza vaccine as an IM injection in the deltoid muscle at any time between Day 1/Week 1 and Day 84/Week 12. If a patient needs to receive the influenza vaccine after Week 12, the optional OCR infusion must be delayed.

Group A1 patients can receive the influenza vaccine at any time at the discretion of the investigator.

Refer to the label for dosing and administration guidance.

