4.7.7 Withdrawal Visits

At the moment a patient meets one or more of the withdrawal criteria (Section [4.8.2](#)), the patient will be regarded as withdrawn from treatment. Patients who withdraw from OCR treatment will need to complete all assessments as shown in [Appendix 1](#) and will enter the SFU. Patients in Group B who do not receive an infusion of OCR in the OOE will not enter SFU.

After entering the SFU, if patients begin an alternative treatment for MS (see Section [4.6.3.1](#) on prohibited therapies), or start treatment with commercial OCR, they will be discontinued from the SFU and from the study.

All patients will undergo a complete final evaluation according to the 'Withdrawal from Treatment Visit' in the Schedule of Assessments ([Appendix 1](#)). Thereafter, all patients will be treated according to individual center practice.

For patients who have withdrawn from the Immunization Study Period or the OOE or who are not eligible for treatment with OCR, the investigator should decide on further treatment of the underlying disease.

However, as sufficient data are not available to inform risks associated with switching to other products, certain treatments for MS, such as lymphocyte-depleting agents or lymphocyte-trafficking blockers (alemtuzumab, natalizumab, fingolimod, dimethyl fumarate, cladribine, daclizumab, cyclophosphamide, azathioprine, etc.), are strongly discouraged for as long as the patient remains B-cell depleted because of unknown effects on the immune system (e.g., increased risk, incidence, or severity of infection) (see also Section 4.6.3.1 for recommendations on alternative treatments for MS).

Please note: at the withdrawal from the Immunization Period or the OOE Period for patients in Groups A and B, an MRI scan will be required only if not performed in the prior 4 weeks.

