5.3.1 Adverse Event Reporting Period

Investigators will seek information on adverse events at each patient contact. All adverse events, whether reported by the patient or noted by study personnel, will be recorded in the patient's medical record and on the Adverse Event eCRF.

New or worsening neurological symptoms not considered MS-related should be recorded on an adverse event page and the monitor should be informed.

After informed consent has been obtained **but prior to initiation of study treatments**, only serious adverse events caused by a protocol-mandated intervention (e.g., invasive procedures such as biopsies, discontinuation of medications) should be reported (see Section [5.4.2](#) for instructions for reporting serious adverse events).

After initiation of study treatments, all adverse events will be reported until Week 48 of the SFU Period. After this period, the investigator should report any serious adverse events that are believed to be related to prior study drug treatment (see Section [5.6](#)).

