Appendix 1 Schedule of Assessments: Table A (cont.)

- 20 **CD4 count:** will be measured separately at screening, and be included in the flow cytometry (FACS) panel at all following visits including every q22-week visit in order to inform eligibility/re-treatment criteria. Other re-treatment labs will be measured as part of IgG and routine safety labs (see item 21 and 22).
- 21 **Flow cytometry:** including CD19 and other circulating B-cell subsets, T-cells (including CD4 cells), NK cells and other leukocytes. On the infusion days, samples should be collected prior to infusion of methylprednisolone.
- 22 **Routine safety labs.** On infusion visits, all urine and blood samples should be collected prior to the infusion of methylprednisolone. At other times, samples may be taken at any time during the visit.
- 23 All patients will receive **prophylactic treatment** with 100 mg of methylprednisolone IV 30 minutes prior to, and an IV or oral antihistamine such as diphenhydramine 50 mg 30–60 minutes prior to OCR infusions. In patients where methylprednisolone is contraindicated, corresponding doses of other IV steroids (e.g., dexamethasone) may be used as premedication. It is also recommended that patients receive an analgesic/antipyretic such as acetaminophen/paracetamol (1 g), 30–60 minutes prior to OCR infusions.
- 24 **Study drug administration:** The investigator must review the clinical and laboratory re-treatment criteria prior to re-dosing patients with study drug at Day 168 (Week 24) and prior to any subsequent OCR infusion.
- 25 Influenza vaccine and post-vaccination assessment for Group A2 only. Influenza can be administered between Weeks 12–20. Post-vaccine assessments must be done after 4 weeks. For patients in Group A2 who are due to receive the influenza vaccine during their country-specific influenza vaccine blackout period, administration of the vaccine should be given prior to the start of this blackout period. Group A1 patients can receive the influenza vaccine at any time at the discretion of the investigator.
- 26 M=Sample to be taken prior to immunization on days when vaccines are administered. On infusion visits, all urine and blood samples should be collected prior to the infusion of methylprednisolone. At other times, samples may be taken at any time during the visit.
- 27 Group A1 only.

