- 26 Influenza vaccine for Group B: Influenza can be administered between Weeks 1 and 12. For patients who need to receive the influenza vaccine after Week 12, the OCR infusion must be delayed. Post-vaccine assessments must be done after 4 weeks. For patients in Group B who are due to receive the influenza vaccine during their country-specific influenza vaccine blackout period, administration of the vaccine should be given prior to the start of this blackout period
- 27 M=Sample to be taken prior to immunization on days when vaccines are administered. On infusion visits, all urine and blood samples should be collected prior to the infusion of methylprednisolone. At other times, samples may be taken at any time during the visit.
- 28 TT-containing adsorbed vaccine refers to the combined tetanus and diphtheria (DT/Td) or tetanus, diphtheria, and acellular pertussis (DTaP/Tdap) vaccines.

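### Group B patients who take no ocrelizumab leave the study at Week 12, so the required 4-week assessment after an influenza vaccination on Days 57–84 falls outside the study as written

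*Protocol*

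**What the plan says.** Protocol 3.1 sets the control-arm calendar: "For Group B, the Immunization Study Period will end at Day 84/Week 12". Those who do not qualify for, or "do not choose treatment with OCR at Week 12 will complete the study at Week 12 and will" not go into safety follow-up. Section 4.7.7 repeats this: "Patients in Group B who do not receive an infusion of OCR in the OOE will not enter SFU".

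Section 4.4.2.5 lets Group B have the influenza vaccine "at any time between Day 1/Week 1 and Day 84/Week 12". Appendix 1, Table B, note 26 agrees ("Influenza can be administered between Weeks 1 and 12") and adds: "Post-vaccine assessments must be done after 4 weeks". For vaccination later than Week 12, both places provide only for moving the ocrelizumab infusion.

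For Group A2, Table A note 25 says "Influenza can be administered between Weeks 12–20", and 3.1 ends the Immunization Study Period (ISP) on Day 169.

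On adverse events, 5.3.1 states: "After initiation of study treatments, all adverse events will be reported until Week 48 of the SFU Period". Section 5.4.2.2 uses the same limit, and 5.6 defines it as 48 weeks after the last dose of study drug.

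In the SAP, the influenza endpoints are measured 4 weeks after vaccination (4.4.2.4) in patients who completed the ISP (4.1.2). Missing immunology values are left out without imputation (4.4, 4.7). Section 4.6.2.1 tabulates events related to each vaccine, by group, as a simple proportion of patients.

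**The concern.** A Group B patient who takes no ocrelizumab and is vaccinated late is covered by two instructions that cannot both be met: complete at Week 12 with no follow-up, and be assessed 4 weeks after the vaccine. Moving the infusion does not help someone who will not have one.

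Two kinds of data are at stake. One is the 4-week titer for secondary objective 4 (Group A2 against Group B). A site that follows the Week 12 exit does not take it; the patient is still an ISP completer, but contributes no influenza result. The other is adverse events after vaccination, which Protocol 3.4.4 lists as a safety outcome for the study immunizations.

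A related asymmetry affects the tables. Group A2 has time left in the ISP after its latest permitted vaccination; Group B need not have any. A crude proportion of patients with influenza-related events in the ISP would then be based on unequal observation.

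**Working it through.** **Day-count convention.** Duration is end day minus start day. For the Group A ISP, 169 − 1 = 168 days, which reproduces the figure in SAP 4.6.1.1.

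**Group B patient who takes no ocrelizumab, vaccinated on day v.**
- Days observed = 84 − v. At least 28 days requires v ≤ 84 − 28 = 56.
- For v = 57 to 84, the days observed run from 27 down to 0.
- The required assessment falls on v + 28, that is Day 85 to Day 112, or 1 to 28 days after completion.
- If the Week 12 visit uses its ±4-day window (Day 80 to 88), the last vaccination day that leaves 28 days is Day 52 to Day 60.
- The affected part of the permitted window is 28 of 84 days, or one third. This is a share of calendar days, not of patients.

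**Ceiling on numbers.** About 100 patients at 2:1 gives 100 × 1/3 ≈ 33 in Group B. The affected group is the part of these who take no ocrelizumab and are vaccinated after Day 56. The documents give neither proportion.

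**End of adverse event reporting.** Sections 5.3.1 and 5.4.2.2 need a safety follow-up Week 48; 5.6 needs a last dose of study drug. This patient has no safety follow-up and no ocrelizumab dose.

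**Time after influenza vaccination inside the ISP.**

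| | Longest | Shortest, nominal days | Shortest, ±4-day windows |
|---|---|---|---|
| Group A2 (Days 85–140, end 169) | 169 − 85 = 84 | 169 − 140 = 29 | 165 − 144 = 21 |
| Group B (Days 1–84, end 84) | 84 − 1 = 83 | 84 − 84 = 0 | 0 |

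A Group A2 patient who skips the extension is followed to about Day 15 + 48 × 7 = 351, which is 351 − 140 = 211 days after a Day 140 vaccination. SAP 4.6.2 places safety follow-up events in the period of the previous dose, here the ISP.

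**Share of Group B event time after Day 84.** Assume events are spread evenly over w days after vaccination. The share is the mean of max(0, v + w − 84)/w over the assumed vaccination days.
- Vaccination even over Days 1–84, w = 28: (1 + … + 28)/28 = 14.5; 14.5/84 = 17%.
- Same, w = 14: 7.5/84 = 9%.
- Same, w = 7: 4/84 = 5%.
- Equal shares at Days 1, 28, 56 and 84: only the Day 84 group is cut, and it loses everything, so 1/4 = 25% for each w.
- Group A2 at nominal days: 140 + 28 = 168, before Day 169, so 0%. With visit windows this is no longer guaranteed.

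These shares describe all of Group B, including patients who enter the extension and whose later events are still collected.

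**The case against.** The best defense is that the 4-week assessment is mandatory, so sites would bring the patient back. SAP 4.4.2.4 defines the endpoint as 4 weeks after vaccination, not by Day 84, so a Day 112 sample from an ISP completer would be analyzable. That is a fair reading, and it means loss of the titer is likely rather than certain. It does not remove the conflict: no visit after completion and no adverse event period is written for this patient.

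A reader might infer that the control arm as a whole loses 17% to 25% of its post-influenza safety data. The documents do not support that. Group B patients who enter the extension remain under observation; on the natural reading of SAP 4.6.2 their later events are tabulated in another period, and 4.6.2.3 plans summaries across all periods. The percentages also rest on vaccination timing that the documents do not give, and seasonality makes an even spread doubtful.

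Nor does every Group A2 patient have at least 29 days in the ISP: visit windows allow 21.

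It is also true that the stated safety objective concerns ocrelizumab, that the tables are descriptive with no hypothesis tests, and that the two ISPs differ in length by design (24 against 12 weeks). These points limit the consequence. They do not justify comparing influenza-related events over unequal windows when a common one is available.

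**Conclusion.** The conflict stands, in a narrow form. As written, a Group B patient vaccinated on Days 57–84 who takes no ocrelizumab completes the study before the required assessment, and has no defined end to adverse event reporting. A titer not taken drops out of the Group A2 versus Group B influenza analysis. The number cannot be derived from the documents.

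The table asymmetry is a separate and broader point: a shortest ISP window of 29 nominal days (21 with visit windows) in Group A2 against 0 in Group B. For extension entrants this is a matter of where events are counted, not of lost data. Any percentage is conditional: about 5% to 17% with even vaccination and a 7- to 28-day event window, or 25% with equal shares at the four visits.

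A reader might go further and conclude that the ISP tables make influenza vaccination under ocrelizumab look worse by a known amount. Fewer counted control events would push in that direction, but the size is unknown. This merits correction because the repair is cheap, not because it threatens the primary endpoint.

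**What to change.** Reconcile Protocol 3.1, 4.7.7 and the synopsis with Table B note 26. A Group B patient not entering the extension should not count as complete until the 4-week post-influenza assessment already required, with the titer and adverse events collected to that date.

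Protocol 1.1.4 and 5.1.1.6 already report ISP results. If that period is finished, the text change cannot recover data. In that case, report how many Group B patients lack a 4-week titer, or 28 days of observation after influenza vaccination, for this reason.

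In SAP 4.6.2.1, add one table of influenza-related events in Groups A2 and B over the same 28 days after vaccination, regardless of the boundary between the ISP and the extension, with days at risk. For Group B, show events before and after any first ocrelizumab infusion separately. Stopping the count at that infusion would leave late-vaccinated extension entrants truncated.

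The cost is a short clarification, up to 4 more weeks in the study for a few patients where that is still possible, and one extra table. No dose or treatment rule changes.

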3.2 END OF STUDY

The end of study is defined as the last patient last visit in the Safety Follow-Up Period.

3.3 RATIONALE FOR STUDY DESIGN

The primary objective of this study is to characterize the effects of OCR on immune responses in patients with RMS as measured by vaccine titers. The randomized, open-label nature of this study is not expected to significantly affect vaccine titers in either Group A or B (active or control, respectively).

3.3.1 Rationale for Specific Antigens

This trial will investigate the effect of B-cell depletion by OCR on primary humoral response, recall response, and persistent acquired immunity to specific antigens.

- A TT-containing adsorbed vaccine will be administered to assess whether one dose of OCR affects the integrity of a T-cell-dependent anamnestic humoral response.
- A 23-valent PPV has been selected to assess a mostly T-cell independent or 'pure B-cell' humoral response for a clinically relevant antigen.
- KLH will be used to test primary humoral neoantigen response as it is a novel immunogen for most individuals.
- An influenza vaccine has been selected to test the ability to mount a humoral immune response to a clinically relevant vaccine.

3.3.2 Rationale for Timing of Vaccinations

Experience with OCR in MS in the Phase II study (Study WA21493/ACT4422G) has determined that the majority of patients are still peripherally CD19-positive B-cell depleted between 12 and 24 weeks post-treatment. Therefore, Day 85/Week 12 is an appropriate time to begin vaccinations in patients to evaluate the effect of peripheral CD19-positive B-cell depletion by OCR on immune response to vaccination.

3.3.2.1 Tetanus Toxoid Adsorbed Vaccine

TT vaccine will be administered as a combined adsorbed vaccine with diphtheria (tetanus-diphtheria [Td] or diphtheria and tetanus toxoid [DT]) or with diphtheria and acellular pertussis (diphtheria-tetanus-acellular pertussis [DTaP] or tetanus-diphtheria-acellular pertussis [Tdap]).

Group A (active) patients will receive a TT-containing vaccine 12 weeks after the first OCR administration. Serum anti-tetanus titers will be measured 4 and 8 weeks after vaccine administration and compared with levels immediately prior to vaccine administration.

Group B (control) patients will not receive OCR during the Immunization Study Period. They will receive a TT-containing vaccine at Day 1/Week 1. Serum anti-tetanus titers will be measured 4 and 8 weeks after vaccine administration (Day 28/Week 4 and

Day 56/Week 8) and will be compared with levels immediately prior to vaccine administration.

3.3.2.2 23-Valent Pneumococcal Polysaccharide Vaccine

The 23-PPV will be administered to Group A (active) patients 16 weeks after the first OCR administration. Serum titers against all 23 serotypes (1, 2, 3, 4, 5, 6b, 7F, 8, 9N, 9V, 10A, 11A, 12F, 14, 15B, 17F, 18C, 19F, 19A, 20, 22F, 23F and 33F) will be measured 4 and 8 weeks after vaccine administration and will be compared with levels immediately prior to vaccine administration.

Group B patients will receive the 23-PPV vaccine at Day 28/Week 4. Serum titers will be measured 4 and 8 weeks after vaccine administration and will be compared with levels immediately prior to vaccine administration.

3.3.2.3 Keyhole Limpet Hemocyanin

Group A (active) patients will receive KLH at 12, 16, and 20 weeks after OCR administration. Serum titers will be measured 4, 8, and 12 weeks after the initial KLH administration (Day 112/Week 16, Day 140/Week 20, and Day 169/Week 24) and will be compared with levels immediately prior to the first KLH administration.

Group B patients will receive KLH at Day 1/Week 1, Day 28/Week 4, and Day 56/Week 8. Serum titers will be measured 4 weeks after KLH administration (Day 28/Week 4, Day 56/Week 8, and Day 84/Week 12) and will be compared with levels immediately prior to the first KLH administration.

3.3.2.4 Influenza Vaccine

Group A (active) patients are to be split and patients assigned to Group A2 will receive the influenza vaccine after OCR administration (refer to Section 3.1 for details on the assignment on patients to Group A1 or A2). Patients can receive the influenza vaccine at any time between Weeks 12 and 20. Serum titers will be measured 4 weeks after the initial vaccine administration and will be compared with levels immediately prior to vaccine administration.

Group B patients can receive the influenza vaccine between Week 1 and 12. If necessary, Group B patients can receive the influenza vaccine after Week 12, in which case the OCR infusion visit must be delayed. Serum titers will be measured 4 weeks after vaccine administration and will be compared with levels immediately prior to vaccine administration.

Group A1 patients can receive the influenza vaccine at any time at the discretion of the investigator.

3.3.2.5 Conjugate Pneumococcal Vaccine Booster (13-PCV)

Group A (active) patients will be split at randomization and approximately 33 patients will be in Group A1 and receive a booster 13-PCV at Day 140/Week 20 (refer to Section 3.1

for details on the assignment on patients to Group A1 or A2). Serum antibody titers will be measured 4 weeks after the booster 13-PCV administration (Day 169/Week 24).

3.3.3 Rationale for Ocrelizumab Dose Selection

The dose of 600 mg of OCR administered intravenously (IV; given as dual infusions of 300 mg on Days 1 (Dose 1 Infusion 1) and 15 (Dose 1 Infusion 2) for the first dose and subsequently as a single infusion of 600 mg every 24 weeks) is under investigation in the Phase III RMS clinical program. This has been selected as a clinically appropriate dose based on the results from Study WA21493/ACT4422g.

3.3.4 Rationale for Group B

In Group B, patients will be eligible for the study provided that they are on no MS-specific DMT or continuing with IFN- β treatment.

Group B patients will enter the study on their current IFN- β MS treatment or remain on no MS-specific DMT until Week 12 at which point they can receive OCR (300 mg \times 2 infusions at Day 84/Week 12 and Day 98/Week 14). The study has been designed with the shortest Immunization Study Period feasible for patients in Group B before they can receive OCR.

